Following the completion of all nurse support appointments, practice staff with experience of recruiting and/or supporting patients recruited to the study will be invited to take part in an interview in order to understand their experiences of delivering the study and working with patients in the study. Views about the website and the study procedures will be sought in order to improve our understanding of the deployment of the programme within primary care and inform future programme development.

Phase 2. RCT

Inclusion criteria. Adult patients with BMI >=30 (or 28 with hypertension or hypercholesterolaemia) documented in the GP case records¹² will be eligible.

Exclusions: Current major mental problems e.g. psychosis (difficulty completing outcomes); very ill or unable to change diet (e.g. severe LVF); pregnancy, or breast feeding; perceived inability to walk 100 metres (physical activity difficult).

Invitation of patients/recruitment. Up to 100 patients in each practice will be randomly chosen from GP electronic records, and invited by letter to a screening appointment to confirm eligibility; with 15-20 patients per practice being recruited to the trial. Patients can also be referred opportunistically when seen in practice nurse or GP clinics. Recruitment will take place over 6 months in up to 44 practices from the South West and South East Hubs of the PCRN.

Randomisation and informed consent. At the screening appointment the practice nurse will take written, informed consent and the patients' details in each practice will be sent to an external randomisation line to allow stratification of randomisation - gender; waist (>102 cm men; >88cm women); BMI >=35; Index of material deprivation score (>median); partner in the household; source of patients (invited by mailing or opportunistically invited). Practice staff will inform patients of their group indicating the nature and timing of contacts (and with the personalised website password as appropriate in the web group).

Planned interventions

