Adherence and predictors of adherence. We will measure intention to change behaviour for each specific behaviour, and other items based on components of the TPB⁵⁶ (attitudes, social norms, perceived behavioural control) ^{2;15;16} ⁵⁶. We will measure behavioural adherence through self report which is likely to strongly predict weight loss³⁵. All website usage is automatically recorded, including frequency and duration of logins, options selected and all data inputted (e.g. weekly goal achievement).

Outcome measurement: At the appointments with the practice nurse (baseline, 6 months, 12 months), the physiological measurements will be performed, and patients weighed; research staff blind to group will also perform a final weight measurement at 12 months. For the few patients who do not provide questionnaire answers we will perform up to 2 emails/mailings, and telephone follow-up of those still not responding.

Socio-Demographic data. Age, gender, education, internet experience, social deprivation indices based on post code will be recorded.

Notes review. All patient's notes will be reviewed to document consultations, returns, time to return, reasons for returns, complications, economic data and any subsequent referrals. ⁵⁷

Sample size. We wish to compare each of the intervention groups primarily with control but also with each other so for our primary outcome (weight) we allow for alpha=0.017 (i.e. 0.05/3) to minimise type I error. For a standardised effect size of 0.33 (i.e. a small effect size, equivalent to 2-3 Kg difference assuming an SD of change of 6.5-7.5 Kg^{6,48}) and 80% power this requires 174 patients per group with complete data, or 654 patients in total allowing for 20% loss to follow-up (hence we will aim to recruit a minimum of 660 patients).

Analyses

Primary analysis: Repeated measures ANOVA for the principal continuous outcomes (i.e. weight) between groups and for the secondary outcomes, controlling for stratification variables.

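### The primary repeated measures ANOVA of weight is tied to neither continuous baseline weight nor 12 months, although the trial is sized on the SD of change

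*Protocol*

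**What the plan says.** The primary analysis is one sentence in the Protocol (Analyses): "Repeated measures ANOVA for the principal continuous outcomes (i.e. weight) between groups and for the secondary outcomes, controlling for stratification variables". It names a model and a covariate set.

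The stratification variables are listed under Randomisation and informed consent: "gender; waist (>102 cm men; >88cm women); BMI >=35; Index of material deprivation score (>median); partner in the household", and also how the patient was recruited. Weight itself is not among them.

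The primary outcome is given as weight, measured at baseline, 6 and 12 months, with no time point singled out. The 12-month weighing is called final and is repeated by blinded research staff.

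The Sample size paragraph works on a different scale. The effect is "equivalent to 2-3 Kg difference assuming an SD of change of 6.5-7.5 Kg". For comparing each web arm with control and the two web arms with each other, "we allow for alpha=0.017 (i.e. 0.05/3) to minimise type I error".

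**The concern.** In a repeated measures ANOVA, a comparison between groups is ordinarily the group main effect. That effect averages over occasions and is judged against between-person variation. If baseline is one of three occasions, a third of the averaged data carries no treatment effect. If only 6 and 12 months are used, the model does not hold baseline weight, and cut-points for waist and BMI replace it only in part. Under both of these readings the error term is close to the SD of weight, not the SD of change on which the trial was sized.

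The group-by-time test is a further reading. It does compare change between groups, but it pools 6 and 12 months. The protocol gives much attention to maintaining weight loss, so it matters whether a positive result could rest on 6 months alone.

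What is at stake is that one sentence allows tests with very different power and meaning, and the choice could be made after the data are seen.

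**Working it through.** **Inputs from the Protocol (Sample size).** Alpha 0.017, taken as two-sided because sidedness is not stated; "For a standardised effect size of 0.33"; SD of change 6.5-7.5 kg, midpoint 7 kg; effect 0.33 × 7 = 2.31 kg; 174 per group.

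**Assumed, not in the document.** SD of weight at one visit (S) 14-20 kg, equal at each visit, with compound symmetry. The correlation between visits is then ρ = 1 − 7²/(2S²). The full effect is present at 6 and 12 months unless stated.

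**The plan's own figure.** The text says "80% power this requires 174 patients per group with complete data". The formula n = 2(z₁₋α/₂ + z₀.₈)²/0.33² gives:
- alpha 0.017: 2(2.387 + 0.842)²/0.1089 = 191.4, so 192 per group;
- alpha 0.025: 174.6, so 175 per group.

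The stated 174 is thus not reproduced at 0.017 and is close to the result for 0.025. That is a separate matter; 174 is used below as the planned number. The next step, "654 patients in total allowing for 20% loss to follow-up", does follow: 174/0.8 = 217.5, so 218, and 3 × 218 = 654.

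**Power formula.** Power = Φ(λ − 2.387), with λ = δ/(σ√(2/174)) and √(2/174) = 0.1072.

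**Change to 12 months (the sizing basis).** λ = 2.31/(7 × 0.1072) = 3.08; power 75.5%.

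**Three other comparisons.**
- A, group main effect over 0/6/12 months: δ = (2/3) × 2.31 = 1.54; σ² = S²(1 + 2ρ)/3.
- B, mean of 6 and 12 months without baseline weight: δ = 2.31; σ² = S²(1 + ρ)/2.
- C, 12-month weight adjusted for baseline weight: δ = 2.31; σ² = S²(1 − ρ²).

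| S (kg) | ρ | A: σ, power | B: σ, power | C: σ, power |
|---|---|---|---|---|
| 14 | 0.875 | 13.40, 9.4% | 13.56, 21.3% | 6.78, 78.6% |
| 16 | 0.904 | 15.48, 7.2% | 15.61, 15.7% | 6.83, 77.9% |
| 18 | 0.924 | 17.54, 5.8% | 17.66, 12.2% | 6.87, 77.4% |
| 20 | 0.939 | 19.59, 4.9% | 19.69, 9.8% | 6.89, 77.0% |

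**Allowing for the stratifiers.** Suppose they explain 30-60% of weight variance (assumed), so that R²S² is taken off σ². For A at S = 14 and 60%: 179.7 − 117.6 = 62.1, σ = 7.88, λ = 1.82, power 28.7%. At S = 20 and 30%, A has 6.7%. The ranges become about 7-29% for A and 14-60% for B.

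**Group-by-time test** (two arms, 2 df, baseline as a level). The within-person error variance is 7²/2 = 24.5. The noncentrality is (174/2) × SS/24.5, where SS is the sum of squares of the three arm differences about their mean. The critical F(2, 692) at 0.017 is 4.10.
- Differences 0, 2.31, 2.31: SS = 3.557, noncentrality 12.63, power 80%.
- Differences 0, 1.155, 2.31: SS = 2.668, noncentrality 9.47, power 65%.
- Differences 0, 2.31, 0, an effect seen at 6 months and gone by 12: SS is again 2.31² × 2/3 = 3.557, power 80%.

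The last line shows that this test does not isolate 12 months.

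**The case against.** The strongest objection is that the usual treatment test, when baseline is a repeated level, is group-by-time. It compares change between groups against within-person error, and the text does not exclude it. The rest of the protocol points the same way: the sizing uses the SD of change, and the conservative intention-to-treat analysis adjusts the variance of change. This stands. A reader might infer that the stated analysis is definitely not the change comparison, or that every reading puts between-person weight in the error term. The document supports neither.

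Two further inferences also go too far. One is that only an omnibus three-group test is planned; the Sample size paragraph states pairwise comparisons and divides alpha for them. The other is that anyone missing a visit is lost from all analysis; a conservative analysis covering those lost to follow-up is described. The document also gives no pattern of regain, so dilution by regain is a possibility and not a forecast.

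The low power figures rest on a weight SD that the protocol does not give, and the stratifiers recover part of baseline weight.

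Finally, contrasts are often left to a statistical analysis plan, and one may exist. That weakens a complaint about omission alone. But the protocol does fix the model and the covariates, on a scale different from its own sizing. A later plan would have to choose among the readings or add to the stated covariates.

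**Conclusion.** The point holds as a failure to tie the primary test to the powered comparison. It does not show that the trial will run the wrong test.

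At 174 per group and two-sided 0.017, the defensible readings run from about 5-10% power (main effect over three visits) and 10-21% (mean of 6 and 12 months without baseline weight) to 65-80% (group-by-time) and 77-79% (12-month weight adjusted for baseline weight). With stratifiers explaining 30-60% of weight variance, the two low ranges rise to about 7-29% and 14-60%.

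The low figures depend on the assumed weight SD. The baseline-adjusted figure hardly does: over S = 12-20 kg and SDs of change of 6.5-7.5 kg it stays at about 77-80%, while A spans 4-16% and B 9-36% before any allowance for stratifiers. The group-by-time figures assume compound symmetry and a two-arm comparison.

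Whatever weight SD is assumed in this range, the wording does not name 12 months and does not use the baseline weight that the trial collects.

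**What to change.** Replace the primary analysis sentence with wording such as: *The primary estimates are the pairwise arm differences in weight at 12 months, from a linear mixed model of weight at 6 and 12 months with arm, visit, arm-by-visit, continuous baseline weight, baseline-by-visit and the stratification variables, and an unstructured within-patient covariance (or a patient random effect). All patients with at least one follow-up weight are included. The differences at 6 months are secondary.*

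Use the same model for continuous secondary outcomes measured at baseline and follow-up in all arms. It cannot serve for measures such as the FFQ and Godin questionnaires, which the control group completes only at 12 months; their analysis should be stated separately.

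The cost is wording only. Baseline weight is already collected in every arm, and no visit, measurement or patient is added. Whether to include a practice effect is a separate question and is not part of this change.

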
- reinforced by pedometer use⁸, or setting personal physical activity goals. The patient can select all subsequent weight loss sessions from a menu which includes coverage of healthy drinking patterns, relapse prevention, and coping with cravings, stress-induced eating, busy times and social pressures.
- Nurse support. Very brief appointments for weight measurement at 6 months and 12 months (final follow-up) will occur as in the control group. In addition all patients will be offered brief face to face behavioural assessments at 2 weeks, 6 weeks, and 3 months. If a rate of weight loss equivalent to 5% weight loss over 6 months is not being achieved or maintained which we anticipate could be up to half the cohort face to face appointments will be made, up to a maximum of 4 more appointments in total in the first year (which is half the number of the average face to face appointments for dietary and behavioural counselling from trials documented in the NICE review⁵). In line with NICE guidance⁵ if 5% weight loss in not achieved Orlistat will be offered; it will be stopped according to standard stopping rules ⁵. Orlistat can also be used for weight maintenance⁵. The purpose of the nurse contacts is to provide reinforcement, and also to be able to help patients address ongoing or new issues where the web has provided limited support. Where issues arise the approach will be to encourage patients to find their own solutions to the problems raised.
- Other features. Based on previous evidence from systematic review of particular strategies to encourage maintenance of weight loss¹¹, patients will asked to participate in web based peer interaction, and to involve the family or spouse to help limit weight regain.

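### The primary model has no practice or nurse term, so nurse effects confined to the web-plus-nurse arm would make standard errors for that arm's two comparisons slightly too small

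*Protocol*

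**What the plan says.** Under *Analyses*, the protocol names one primary method for weight and for the secondary outcomes: a repeated measures ANOVA between groups, "controlling for stratification variables". *Randomisation and informed consent* lists the stratifiers: gender, waist, BMI, deprivation score, partner in the household and source of patient. Practice is not among them. Allocation is of individual patients through an external line.

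*Invitation of patients/recruitment* plans up to 44 practices, "with 15-20 patients per practice being recruited to the trial". Nurse contact differs by arm (*Planned interventions*):

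- **Web with nurse support:** "In addition all patients will be offered brief face to face behavioural assessments at 2 weeks, 6 weeks, and 3 months", then up to 4 more appointments for patients who are not losing enough weight.
- **Web with minimal support:** one 10-minute face-to-face consultation at 2 weeks, three online contacts and up to two telephone contacts.
- **Control:** under 5 minutes of structured advice from the practice nurse, who is told not to go beyond it.

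Nurses weigh patients in all arms at 6 and 12 months. *Sample size* sets "alpha=0.017 (i.e. 0.05/3) to minimise type I error", because all three pairwise comparisons are planned. It makes no allowance for clustering and gives no ICC.

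**The concern.** Patients in the supported arm of a practice are likely to see the same nurse, or one of a few. If nurses differ in how well they help people lose weight, those patients' outcomes are correlated, while outcomes in an arm with little nurse contact are not, or much less so. This is partial nesting: clustering in one arm of an individually randomised trial. The stated model treats all patients as independent given the stratifiers, so it would understate the variance of the supported arm's mean.

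Two of the three planned comparisons involve that arm. Their confidence intervals would be somewhat too narrow, and their tests would exceed the 0.017 level that the protocol set to limit type I error.

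**Working it through.** **The plan's own figure.** The sample size section states "80% power this requires 174 patients per group with complete data". With a standardised effect of 0.33 and two-sided alpha 0.017, z = 2.387 and n = 2 × (2.387 + 0.842)² / 0.33² = 191.4, so 192 per group, not 174. At 174 per group, power is Φ(0.33/√(2/174) − 2.387) = Φ(0.691) = 75.5%. Two-sided alpha 0.025 gives 175, close to the stated figure. The loss-to-follow-up step does reproduce: 174/0.8 = 217.5, so 218, and 3 × 218 = 654. The shortfall is a separate matter. Below, 174 serves only to set the number of completers per practice.

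**Inputs from the protocol.** 174 completers per arm; up to 44 practices; 660/44 = 15 patients per practice, or 660/20 = 33 practices at 20 each; alpha 0.017, taken as two-sided because sidedness is not stated.

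**Assumed.** ICC of 0.01, 0.05 and 0.10 within practice in the supported arm; independence in the comparator arm; patients of that arm in one practice forming one cluster; equal arm counts within practices.

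**Formulas.**

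- Cluster size m = 174/44 = 3.95 or 174/33 = 5.27.
- Design effect in the supported arm: DE = 1 + (m − 1) × ICC.
- True over model standard error: r = √((DE + 1)/2).
- Actual type I error: 2 × (1 − Φ(2.387/r)).

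Worked case, 44 practices and ICC 0.05: DE = 1 + 2.95 × 0.05 = 1.148; r = √1.074 = 1.036; 2.387/1.036 = 2.303; type I error 0.0213.

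| ICC | 44 practices: r | type I error | 33 practices: r | type I error |
|---|---|---|---|---|
| 0.01 | 1.007 | 0.0178 | 1.011 | 0.0182 |
| 0.05 | 1.036 | 0.0213 | 1.052 | 0.0233 |
| 0.10 | 1.071 | 0.0259 | 1.102 | 0.0303 |

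**Unequal arm counts.** Practice is not a stratifier, so arm counts within a practice will vary. With 660 × 0.8 = 528 completers, or 12 per practice over 44 practices, the effective cluster size is 1 + 11/3 = 4.67. The type I errors become about 0.018, 0.022 and 0.028, within the ranges above.

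**Simulation.** 40,000 null two-arm trials per scenario, 174 per arm, unadjusted t-test, a single endpoint:

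- Practice effect in the supported arm only, ICC 0.05: type I error 0.020-0.024. ICC 0.10: 0.025-0.033.
- Practice effect shared by both arms, ICC 0.01 to 0.10: 0.0165-0.0175 when arms are not balanced within practice, and 0.012-0.017 when they are. There is no inflation.

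**Family-wise error.** For three pairwise comparisons at 0.017 each, simulated with the 4.67 cluster size, it is 0.045 without clustering, 0.046 at ICC 0.01, about 0.05 near ICC 0.03, 0.054 at 0.05 and 0.063 at 0.10.

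**The case against.** A reader might infer that, because patients are recruited in practices and the model omits practice, the standard errors are too small and the 0.017 level is broken. The protocol does not support that. Randomisation is by individual, practices are not allocated to arms, and a practice effect shared by the arms cancels in the comparison. Only an arm-specific effect inflates the error, and the protocol gives no evidence of its size.

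The design also limits such an effect. Practice nurses see patients in every arm, the supported sessions are brief and follow a structured guide, and both intervention arms use a website as the main content. The protocol never says that a practice has one nurse for the trial; with several nurses the clusters would be smaller. An ICC of 0.10 has no support in the text. Bonferroni across three correlated comparisons leaves some slack, so the overall 0.05 is kept up to an ICC of about 0.03.

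All of this stands, and it makes the point conditional and modest. It does not remove it: seven possible behavioural visits in one arm, against brief advice in another, is a setting in which arm-specific nurse effects are plausible.

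It can also be said that the choice of standard errors belongs in a statistical analysis plan, which is not at hand and may add the term. But the protocol does name the model and its adjustment variables, and practice is in neither.

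**Conclusion.** The point holds in a conditional form. The stated primary model makes no allowance for nurse effects confined to the web-plus-nurse arm. If they exist, the two comparisons involving that arm have slightly understated standard errors: negligibly at an ICC of 0.01, by 4-5% at 0.05, and by 7-10% at 0.10. The comparison of minimal support with control is not affected by this mechanism.

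The sizes rest on an assumed ICC, on 33 to 44 practices, on about 4 to 5 completers per arm per practice, and on supported patients in a practice forming one cluster. They show what could happen under the stated model, not that the level is breached. The reason to act is that the stated model can only err towards too much certainty if nurse effects are specific to this arm, and the remedy is cheap.

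**What to change.** In the primary analysis sentence, add that standard errors will allow for clustering by practice, by one of two routes:

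- practice-clustered robust standard errors with small-sample degrees of freedom; or
- a random practice effect specific to the nurse-supported arm.

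A practice intercept common to all arms is not enough, because it absorbs only the effect that already cancels. In simulation, practice-clustered standard errors gave a type I error of about 0.016-0.018 in every scenario, at almost no cost when there was no nurse effect. With about 4 patients per cluster, the variance component in the second route would be weakly estimated, which favours the first.

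The cost is one clause, plus slightly wider intervals for the nurse-arm comparisons if nurse effects exist. No new patients are needed. The analysis does need each patient's practice, which should be at hand because details are sent for randomisation from each practice. This point requires no other change to the model and does not endorse the stated sample size.

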- **3) Web intervention with minimal face to face support.** This group aims to provide a very brief intervention with minimal face to face contact time which therefore could be applied more rapidly and extensively in the NHS. Patients will work through the website, will be prompted to use it regularly by email, and brief face to face contact for weighing only at 6 and 12 months as in the control group. In addition this group will have a brief (10 min) face to face consultation at 2 weeks to confirm the physical activity and dietary targets, 3 brief online contacts at 1, 2, and 3 months and up to 2 further telephone contacts (i.e. 3 brief additional personal contacts compared with the control group until final follow-up) for patients not losing 5% of weight.

Support and training for Nurses. We have shown in piloting that nurses can learn to use the structured intervention materials both easily (i.e. requiring relatively little training) and effectively. The web pages for nurses a) provide a brief overview of the rationale, philosophy and structure of the intervention, b) provide a structured guide to the content of each patient support session c) give nurses access to an overview of their patients' progress and the content of each session, and d) send email reminders and notifications to nurses when patient support sessions are required (at timed intervals and if patient not using website or not losing weight), and include a tick-box record for nurses to complete logging what support has been provided.

Proposed time period for retention of relevant trial documentation

Trial documentation will be kept for 15 years.

Proposed outcomes/data collection (at baseline and unless specified at 6 and 12 months). Primary outcome measure:

Weight (primary outcome): lightly clothed, without shoes, at the same time each day, and using automated Tanita digital scales (which will also allow measurement of body composition).

Secondary outcome measures:

Food and drink consumption and physical activity (at baseline and final follow-up): These behavioural measures (and intentions/attitudes to behaviour – see below) will be made in the intervention group at baseline and follow-up but in the control group only at final follow-up to avoid

such measurement being a prompt for behaviour change in the control group.

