Physical activity: Using the validated Godin leisure time physical activity questionnaire and physical activity monitors^{29,30}. Activity monitors have well documented limitations in validity, although may provide an adequate proxy to estimate between group differences. One third of the sample will in addition be randomised to wear the Actiheart monitors which will allow much more precise estimation of physical activity.

Food and drink consumption: Using validated brief FFQs for major food groups and also alcohol developed by our group for use in primary care. ^{31,32}

Indices of the metabolic syndrome (waist,BP,glucose,TG,HDL)³³⁻³⁶. Individuals with the metabolic syndrome are at particular risk. We will report the number (%) in each group using a definition of 3 out of 5 of high measurements³⁷, and a continuous outcome based on the mean z score for each individual (or mean rank as appropriate) - supported by empirical evidence of a close factor structure among the variables³⁸;

Waist: nurses will measure waist midway between the lower ribs and the iliac crests³⁹ also height, hip, skin fold thickness – to allow estimation of BMI, waist hip ratio, and fat mass ^{40; 41}

Blood pressure (BP) 42: Measured 3 times (after 5 min) using a validated OMRON 43;44;

Serum measures: Liver function tests (particularly to monitor non alcoholic fatty liver disease), fasting serum cholesterol/HDL/LDL/triglyceride (TG) ^{41,45,46} ⁴⁷ glucose, HbA1c and insulin ^{48,49} (which would be expected to be modified by weight reduction); also ferritin (important to measure due to reducing cereals (a key source of iron) in the low carbohydrate diet)

Patient satisfaction and understanding. Simple Likert scale responses are reliable and valid.⁵⁹; **SF36**⁵⁰: The eight scales have been shown to be valid in a wide range of conditions in primary care; **EuroQol**^{51;52} (EQ-5D): the EuroQol provides a measure of quality of life for economic analysis;

Psychological status: Using the Hospital Anxiety and Depression scale⁵⁰ and brief state anxiety.⁵³ Obesity is associated with psychological morbidity,⁵⁴ and distress, anxiety and depression may be changed by physical activity⁵⁵;

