Subgroup analyses: Estimates of effect in subgroups according to baseline waist measurement (high vs low waist), and the presence of the metabolic syndrome (syndrome vs no syndrome) will be explored. Assessments will be made of outcomes (weight, reported behaviour change, measured behaviour change) according to website usage and changes in psychological variables (e.g. change in components of the TPB) and according to the type of diet chosen by patients. **Other analyses:** Weight changes will be plotted against changes in metabolic variables to compare slopes between groups.

The most conservative intention to treat analysis will assume that those patients lost to follow-up have regained their initial weight, with an adjustment to allow for the variance (if exactly the same measurements were used there would be no variance of change for the missing data, and so would underestimate the overall variance of change). The study will be reported in accordance with the CONSORT (Consolidated Standards of Reporting Trials) statement.

Economic analysis. The cost of intervention and follow-up related service use, including the time taken to train staff, surgery attendance, admissions and referrals, will be collected in the trial. Resource use data will be collected by notes review, GP and nurse documentation (e.g. of consultation time) and patient self-report.

Qualitative process analysis: During months 18 to 24 of the study we will interview 12-16 patients from both the intervention groups immediately after the 12 month appointment, purposively sampling for diversity in baseline characteristics (age, gender, internet experience), adherence levels and outcomes. Interviews will be tape-recorded, fully transcribed and analysed by thematic analysis ¹⁴ with constant comparison⁵⁸ of emerging themes based on intervention group and all the factors used for purposive sampling. The aim will be to identify processes that may have influenced intervention acceptability and effectiveness for different patients.

Risk and benefits for trial participants

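### Effect modification by metabolic risk is explored only through a syndrome/no-syndrome split; a term for the continuous baseline metabolic score should be added beside it

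*Protocol*

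**What the plan says.** Under Analyses, the Subgroup analyses paragraph of the protocol names two baseline characteristics as possible effect modifiers, and both are binary. One is high or low waist. The other is "the presence of the metabolic syndrome (syndrome vs no syndrome) will be explored".

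The category is defined under Secondary outcome measures, in the item on the metabolic syndrome: "We will report the number (%) in each group using a definition of 3 out of 5 of high measurements". The same sentence also plans "a continuous outcome based on the mean z score for each individual", with a mean rank as the alternative, and supports it by evidence that the components share a close factor structure. The five components are waist, blood pressure, glucose, triglycerides and HDL. Table 1 lists all five at baseline in each of the three groups, so a baseline score can be computed for any patient with complete measurements.

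The nearest continuous analysis is under Other analyses: "Weight changes will be plotted against changes in metabolic variables to compare slopes between groups". It uses changes after randomisation, not baseline risk.

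**The concern.** The protocol treats the five components as one continuous dimension when it measures outcome, but uses only the category when it asks whether the effect depends on metabolic state. The category cuts each component at a threshold and then cuts the count at three. A patient just below the line on three components is therefore grouped with one who is well below it on all five.

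If the benefit of the web programme rises or falls steadily with metabolic risk, this coding makes the trend harder to see, even when the two subgroups are of similar size. What is at stake is the sensitivity of one exploratory analysis. The comparison of weight between the groups does not depend on it.

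**Working it through.** The protocol gives no figure for this analysis, so there is none to reproduce. The check asks how much of the score's information the split keeps, and what that means for power.

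**Inputs from the protocol.** The syndrome is at least 3 of 5 components; the score is the mean z score of those five; 174 patients per group have complete data; the planned effect is 0.33 SD (both under Sample size). The 174 is taken as stated. Whether it follows from the stated alpha is a separate matter and does not change the comparison of codings.

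**Assumptions, not in the protocol.** Five normal components with equal pairwise correlation 0.1-0.4; waist high in 95%; each of the other four adverse in 25-70%; effect modification linear in the score; two-sided 5% test; one pairwise comparison (2 × 174 = 348 patients).

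**Step 1: information kept.** For a modification linear in the score S, an indicator D keeps the share r² = corr(D, S)². The most favourable single cut of a normal score, at its median, keeps φ(0)²/(0.5 × 0.5) = 0.3989²/0.25 = 0.637, a loss of 36%. The 3-of-5 rule is not a direct cut of the score, so it was simulated with 400,000 patients per scenario:

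| Correlation | Adverse rate, other four | Syndrome prevalence | Kept | Lost |
|---|---|---|---|---|
| 0.1 | 25% | 26% | 37% | 63% |
| 0.1 | 40% | 50% | 44% | 56% |
| 0.1 | 50% | 65% | 43% | 57% |
| 0.1 | 70% | 88% | 28% | 72% |
| 0.4 | 25% | 28% | 48% | 52% |
| 0.4 | 40% | 48% | 54% | 46% |
| 0.4 | 50% | 61% | 53% | 47% |
| 0.4 | 70% | 82% | 41% | 59% |

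Over this grid the loss is 46-72%, or roughly 45-70%. A second grid, with other thresholds and correlations from 0 to 0.5, gave 41-73%.

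**Step 2: in patients.** If half is kept, 348 patients carry the interaction information of 348 × 0.5 = 174. At 28% and 54% kept, the figures are 97 and 188.

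**Step 3: power.** The standard error of the interaction per SD of score is 2/√348 = √(2/174) = 0.107 SD of weight change. For a gradient g, power is Φ(g√r²/0.107 − 1.96), with r² = 1 for the score. The split is shown for 30-55% kept:

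| Gradient g (SD per SD) | Score | Split |
|---|---|---|
| 0.10 | 15% | 7-10% |
| 0.15 | 29% | 12-18% |
| 0.30 | 80% | 34-55% |

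**Step 4: how large these gradients are.** With an average effect of 0.33, a gradient of 0.30 means that the effect vanishes 0.33/0.30 = 1.1 SD below the mean score and reaches 0.33 + 0.30 = 0.63, nearly double, 1 SD above it. That is extreme. The rows for 0.10 and 0.15 are the more modest cases.

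**The case against.** The strongest reply is that the split answers a different and legitimate question. The protocol's remark about raised risk is made of people who have the syndrome, not of a gradient, and the subgroup analysis uses that same category. The efficiency argument also assumes its conclusion. Squared correlation is symmetric, so if the effect truly differs by diagnosis, the score would keep only the same 28-54% and the split would be the efficient coding. This stands. It is why the score term belongs beside the split and should not replace it.

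A reader might infer that the protocol contradicts itself by computing a score and then ignoring it. It does not. The score is named as an outcome, and using its baseline value as a modifier is a modest extension. A reader might also infer that a null result will be reported as no difference. The protocol promises exploratory estimates only and sets no test or decision rule for them.

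It can also be said that modelling form is often left to a statistical analysis plan, which is not shown here. That carries less weight, because the protocol itself names the binary coding. Nothing in it forbids a continuous supplement, however.

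**Conclusion.** The point holds as a low-priority improvement. The only planned look at effect modification by overall metabolic state is binary, although a continuous score of the same components is already planned and is available at baseline. The comparison of slopes does not fill the gap.

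Under a roughly linear gradient the split loses about 45-70% of the score's information. The range rests on assumed prevalence, correlations and normality. It is tempting to say flatly that half the information is thrown away, but the documents do not support that: they give none of these inputs, and the loss does not arise if the effect steps at the diagnosis. With modest gradients both codings would usually miss the modification, so the gain in practice is limited. The primary conclusion and the sample size are unaffected.

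**What to change.** In the Subgroup analyses paragraph, add one sentence: the weight model will also include a treatment by baseline metabolic score interaction, using the mean z score (or mean rank) of the five components at baseline, each oriented so that higher is worse. Keep the syndrome/no-syndrome estimates as planned and report the two together. Check linearity with a plot of effect against score or estimates by tertile. Label all of it exploratory.

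The cost is one sentence and one set of model terms, with no new data. The downsides are one further exploratory analysis, reliance on a linearity assumption, and low power for modest gradients, which the report should acknowledge when it interprets a null result.
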